## 6.4 Summary of known and potential risks and benefits

Patients that will be included are not vulnerable or at high risk of getting hurt, the devices only interact with intact skin for a maximum of one hour and precautionary measures are taken as

described in Section 12. Therefore, no severe adverse events are expected in this study. Several precautionary measures are taken to mitigate possible negative effects in the unlikely event that the device does not function as expected.

Patients will not directly benefit from participating in the sense that it may cure their disorder. The tremor is expected to be suppressed when the orthosis is properly fitted, but this effect will not last after detaching the orthosis. Patients' satisfaction with the device will be assessed, which is a valuable input for the further development of the orthosis. Their feedback, as assessed with the satisfaction questionnaire, will help to optimize the design of the orthosis. A more thorough risk and benefit analysis is described in *IMDD chapter 5*.

## 6.5 Description and justification of route of administration and dosage

A custom verified CRF software package, which also includes an API to acquire the motion and video data, will determine the randomization process of the study procedure.

- 1. Place the orthosis on the table parallel to the arm.
- 2. Slide the elbow into the elbow cuff, the humeroradial joint of the elbow must be aligned with the joint on the orthosis, which connects the sliding parts with the cuff.
- 3. Fasten the elbow cuff by hooking the fastener in the designated slot. Adjusts the tightness of the strap to where the cuff fits secure yet comfortable.
- 4. Slide the handpiece, using the extension element, to an extent where the handpiece is level with the center of the palm.
- 5. Place the hand with the dorsal side in the hand piece.
- 6. Put the thumb between the two straps and fastens the hand piece by hooking the fastener in the designated slot. Fasten the strap to where the cuff fits secure yet comfortable.

More detailed instructions on how to put on the orthosis can be found in Appendix II of the IMDD.

## 6.6 Dosages, dosage modifications and method of administration

See section 6.5.

## 7. METHODS

## 7.1 Study parameters

## 7.1.1 Main study parameter

- Quantification of tremor severity will be based on the TETRAS scale, from which 7 tasks (postural out-stretched arms, postural wingbeat, finger-to-nose, eating, drinking, pouring, Archimedes spiral) are selected that accurately represent the obstruction that ET patients experience in daily life. A TETRAS score is rated on the baseline, sham and intervention conditions. Combining the 7 tasks from the TETRAS scale, a maximum scoring of 28 points can be achieved per condition.
- The co-primary quantification of tremor amplitude will be based on movement data from an Inertial Measurement Unit (IMU). Again, the same 7 tasks (postural out-stretched arms, postural wingbeat, finger-to-nose, eating, drinking, pouring, Archimedes spiral) are used to compare baseline, sham and intervention conditions. A measure for overall tremor amplitude is calculated per test subject, for every selected TETRAS task.

## 7.1.2 Secondary study parameters

- The secondary study parameter, patient's satisfaction, will be scored to test patient satisfaction with regards to comfort and usability of the orthosis with the Dutch Quebec User Evaluation of Satisfaction with Assistive Technology (D-QUEST). This questionnaire consists of 8 questions about the device itself and 5 questions about the service of the manufacturer. Only questions about the device itself will be questioned. Satisfaction is measured on a 1-5 scale, ranging from 'completely not satisfied' to 'very satisfied'. Additional questions, provided by STIL, will be asked to examine comfort, usability, willingness to wear and possible adverse-effects more detailed.
- The other secondary study parameter, product safety, will be collected by the principal investigator using the Dutch version of NCCIH's Adverse Events Report Form. This form is used to report the severity, relationship to the study, taken action, outcome of the AE and whether it was expected or not.

## 7.1.3 Other parameter

 Another parameter, health-related quality of life, will be assessed using EQ-5D-5L. This questionnaire combines a descriptive system and a visual analogue scale to used health-related quality of life, which could possibly intervene with the patient's satisfaction.

## 7.2 Randomisation, blinding and treatment allocation

Tremor severity will be assessed in three situations: without wearing the orthosis (baseline), with the sham orthosis (sham) and with the anti-tremor orthosis (intervention). An algorithm within the CRF software, which includes the API that is used to acquire the motion data, will randomly determine the order of the sham device and intervention. Only the investigator can see which device is selected, thereby blinding the patient. The investigator will obtain the selected device,

using color-coded tabs, and attach it to the patient's arm/hand. Both the devices will have a comparable look and weight (see *IMDD chapter 1.1.i*).

Tremor amplitude can be affected by adding passive weight. By evaluating the sham device, the effects of the weight of the orthosis on tremor suppression will be taken into account. It is also used to evaluate the possible placebo-effect on tremor reduction. Because the investigator knows which variant is being tested, the data will be placed with the corresponding variant in the digital CRF. The patient will be seated in such way that it is not possible for him/her to view the CRF. This eliminates the need to decode the collected data.

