## 3. STUDY DESIGN

This single-blind randomized crossover study will take place at the neurology department of the Reinier de Graaf hospital in Delft.

Tremor severity and amplitude will be measured in three conditions: without orthosis (*baseline*), with a sham-device (*sham*), and with the anti-tremor orthosis (*intervention*). The order of the devices will be randomly assigned by a software specifically designed to aid the investigation. The sham device looks and weighs the same as the anti-tremor orthosis, however it does not contain the working mechanisms used to suppress the tremor. The patient does not know the order of the devices. In this way, single-blinding is guaranteed.

Health-related QoL will be assessed prior to the start of testing with the orthosis, as it could possibly intervene with patient satisfaction. Tremor severity and satisfaction with the devices will be assessed after using a device.

A schematic overview of the study design is depicted in Figure 2. Patient inclusion will be evaluated based on the criteria described in Section 4. Patient inclusion is executed in two steps: first by evaluation of a questionnaire which the patients fill in remotely, and second by a physical evaluation during an appointment in the hospital.

During this appointment in the hospital, patients are asked to perform 7 movement tasks. The movement during tasks will be registered with motion sensors and video-recorded to allow evaluation afterwards.

When the principal investigator is confident that a patient is eligible and he/she is willing to participate, the next part of the appointment – i.e. testing the orthosis and the sham-device – will follow directly. The earlier obtained results of the 7 tasks will be used as the baseline condition. If the principal investigator is unsure if the patient is eligible, the patients is sent home after max. 1 hour. Additional video analysis will determine if the patient is eligible to continue with testing the orthosis. If so, the patient is invited for a second appointment of max. 2 hours, where again is started with 7 movement tasks without orthosis (baseline), followed by testing the orthosis and the sham device in random order.

This protocol allows for minimal impact on the patients, since only a single visit of two hours to the hospital could be sufficient. The study has started in March 2022 and should be finished by December 2022.

Figure 2: Flowchart of the study design

CONFIDENTIAL

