## 7.3.4 Tremor severity assessment using TETRAS

The principal investigator will quantify the tremor severity using the TETRAS scale. The principal investigator is adequately trained to carry out this assessment. To minimize investigator bias, a second opinion from an independent neurologist will be consulted. These movements and postures are derived from the TETRAS scale  and patient will be asked to perform them for 30 seconds:

- **Eating with a spoon:** Using a spoon to bring peas from a bowl on the table to the mouth. This is an adaptation from the TETRAS scale, as it usually does not specify which solids or liquids must be used to assess eating with a spoon.
- **Drinking from a cup:** Bringing a cup (8 cm tall, filled with water to 1 cm from top) from the table to the mouth to drink water.
- **Pouring:** Pouring a water filled plastic cup (8 cm tall, filled with water to 1 cm from top) into another cup (8 cm tall) that is unsupported on the table.
- Forward outstretched posture: Subjects will bring their arms forward, slightly lateral to midline and parallel to the ground. The wrists should also be straight and the fingers abducted so that they do not touch each other (Figure 6).
- Lateral "wing beating" posture: Subjects will abduct their arms parallel to the ground and flex the elbows so that the two hands do not quite touch each other and are at the level of the nose. The fingers are abducted so that they do not touch each other (Figure 6).

Figure 6. Forward outstretched posture

Lateral wing beating posture

- **Finger-nose-test:** Subjects extend only their index finger. They then touch the examiners finger located to the full extent of their reach, which is located at the same height (parallel to the ground) and slightly lateral to the midline. Subject then touch their own nose (or chin if the tremor is severe) and repeat this back and forth.
- Archimedes spiral: Subjects are asked to copy an Archimedes spiral using a ballpoint pen that approximately fills an A6 sheet of paper (Figure 7). The lines of the spiral should be approximately 1.3 cm apart. The pen should be held in such way that no part of the limb touches the table.

*Figure 7.* Archimedes spiral. The patient will be asked to draw a spiral between the lines, connecting the two dots.

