## 7.3.7 Reporting Adverse Events

During the entire visit, the principal investigator will report every observed adverse event using the Adverse Event (AE) Report Form. This form will specify the severity, relation to the study intervention, the taken action, the outcome, the expectancy and whether the event was a SAE of the AE. If SAEs have been observed, they must be reported by the sponsor

though the web portal of *ToetsingOnline*, more information can be found in Section 8.

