## **11.1.3** Procedures for handling and storing data and documents during the investigation

The following sections describe the handling and storage of data and documents for specific stages of the investigation.

Inclusion procedure

The inclusion questionnaire and informed consent that were collected during the inclusion procedure will be stored at the hospital in a locked cabinet. Only the investigator(s) will have access to these hardcopy files.

The motion data and videos gathered during the inclusion procedure will be labelled with the 3-digit ID. After each inclusion session, all encrypted video data is transferred to the secured hospital network drive. All questionnaire data, and other commentary from the investigator, is stored in Castor EDC.

• Study procedure

The videos collected during the study procedure will, again, be stored on an encrypted hard drive. Videos will only be viewed at the hospital's location. These videos can be consulted in case abnormalities have been observed in the TETRAS rating by the principal investigator. The tremor will be rated using TETRAS, the random 3-digit code will be used to assign the scores to the patients. Collected motion data will be pseudonymised and will only use the randomly assigned 3-digit ID code to connect them to the patient. The IMU/video data will be saved as followed: ID code\_task\_condition (e.g. 313 Eating Baseline).

The D-QUEST questionnaire will contain no names or any other information which could directly lead to the patient, it will again make use of the 3-digit code. This hardcopy file of the questionnaire will be stored at a secure site of the hospital. All the keys used during this phase will again be safeguarded by the principal investigator.

Data analysis

Analysis of the clinical investigation data will primarily be executed by the principal investigator on the laptop.

In case expert input needs to be gathered outside of the institution, pseudonymized motion data can be transferred via an encrypted USB device. Motion data cannot be traced back to the patient.

Only under supervision of the principal investigator may the video data be viewed by authorized persons/external experts, and only at a secure site within the hospital. Video data will never leave the premises of the hospital.

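### The TETRAS co-primary has no masked rater, so its sham-versus-orthosis comparison is open to rater expectation

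*Protocol*

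**What the plan says.** - **Who is blinded.** Protocol section 3 rests its blinding claim on the patient alone: "The patient does not know the order of the devices. In this way, single-blinding is guaranteed". Section 7.2 agrees: "Only the investigator can see which device is selected, thereby blinding the patient". The same investigator picks the device by coloured tabs and fits it.
- **How data are stored.** Section 7.2: "Because the investigator knows which variant is being tested, the data will be placed with the corresponding variant in the digital CRF". It presents the absence of coding as a convenience: "This eliminates the need to decode the collected data".
- **Who scores.** Section 7.3.4 gives the TETRAS scoring to the principal investigator. Section 7.3.7 adds: "During the entire visit, the principal investigator will report every observed adverse event". Section 11.1.3 has the principal investigator carry out most of the data analysis as well.
- **The safeguard.** Section 7.3.4, with the stated aim of limiting investigator bias: "a second opinion from an independent neurologist will be consulted".
- **The videos.** Section 11.1.3: "The IMU/video data will be saved as followed", followed by a pattern of ID code, task and condition. On their use in the device sessions: "These videos can be consulted in case abnormalities have been observed in the TETRAS rating by the principal investigator".
- **Purpose of the sham.** Sections 5.1 and 7.2 use it to separate the dampers' effect from device weight and from placebo.

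**The concern.** TETRAS is scored by eye. Appendix I uses distance bands for limb tremor and verbal grades for the spiral and the daily-life tasks. A rater who knows which device is worn and expects the dampers to work can lean towards the lower of two adjacent scores. Random order and patient blinding do not remove that lean, because it follows the device and not the period or the patient's belief.

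The sham-versus-orthosis contrast is the comparison meant to isolate the dampers. If the rater is not masked, an observed TETRAS difference mixes a damper effect with rater expectation, and no later analysis of the same scores can separate the two. Who rates, who is masked and how files are labelled are matters of conduct that this protocol itself settles. They are not details left to an analysis plan.

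**Working it through.** **Step 1. Can anyone who scores TETRAS be masked under the protocol as written?**

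| Possible rater | What the protocol provides | Masked? |
|---|---|---|
| Investigator who fits the device (7.2) | Sees the allocation and files data under the true variant | No |
| Principal investigator (7.3.4, 7.3.7) | Scores TETRAS; reports events for the whole visit | No provision for masking |
| Independent neurologist (7.3.4) | Gives a second opinion; coverage, masking and weight in the endpoint not stated | Not stated; file names (11.1.3) would disclose the condition |

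No row contains a masking step.

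**Step 2. Reproduce the planned sample size (section 4.4).** Inputs: a 4-point reduction, SD 5 in each condition, correlation 0.5, two-sided alpha 0.05/4 = 0.0125, power 0.80.

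- SD of the difference = √(25 + 25 − 2 × 0.5 × 25) = 5, so dz = 4/5 = 0.8.
- At n = 21: noncentrality = 0.8 × √21 = 3.666, critical t on 20 df = 2.744, power = 0.8100.
- At n = 20 the power is 0.783, so 21 is the minimum. This matches the protocol.

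**Step 3. Put an assumed rater lean into the same test.** Let the true sham-versus-orthosis difference be zero and let the rater favour the orthosis by b points in total over the seven tasks. The noncentrality is (b/5) × √n. The rejection rate is the two-sided noncentral-t probability beyond 2.744 (n = 21) or 2.700 (n = 25). The values of b are assumptions; the protocol gives none.

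| Lean b (of 28) | Per task (b/7) | Rejection rate, n = 21 | Rejection rate, n = 25 |
|---|---|---|---|
| 0 | 0 | 0.0125 | 0.0125 |
| 1 | 0.14 | 0.050 | 0.060 |
| 1.75 | 0.25 | 0.155 | 0.195 |
| 3 | 0.43 | 0.515 | 0.620 |

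For scale, 1.75/4 = 44% of the planned 4-point effect. The smallest observed mean difference that reaches significance at n = 21 is 2.744 × 5/√21 = 2.99 points.

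**Step 4. Viewing load for masked scoring.** Device clips: 25 patients × 2 devices × 7 tasks × 30 s = 175 minutes. With baseline clips: 25 × 3 × 7 × 30 s = 262.5 minutes, about 4.4 hours. Both are single playback and exclude scoring time.

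**The case against.** The trial openly declares itself single-blind, and several stronger readings go beyond the text.

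- **The second opinion is unmasked.** A reader might infer this, but section 7.3.4 is silent. The file-naming rule governs storage and does not say what a second rater is shown. What stands is that masking is not provided for and that the names as written would defeat it.
- **Videos are viewed only after an abnormality.** Section 11.1.3 says they can be consulted then; it does not exclude other use. Section 3 records the tasks for later evaluation, and Appendix I refers to scoring from footage. No text makes such viewing systematic for the device conditions or masks it.
- **The person who fits the device is the person who scores.** Section 7.2 speaks of the investigator, section 7.3.4 of the principal investigator, and the protocol never equates them. Section 7.3.7 supports the principal investigator's presence, not directly knowledge of the allocation, and the two devices look alike. The link is likely but inferred. Even if they are two people, no step masks the scorer.
- **A 3-point lean guarantees significance.** It does not: 2.99 points is the critical observed mean, so an expected shift of 3 points rejects in about half of trials. Such a lean, 0.43 per task on average over all seven tasks, is also sizeable on a scale partly anchored in centimetres.
- **The IMU co-primary is a counterweight.** This stands. It makes the same comparison by sensor, so a result confined to TETRAS would be visible as such.

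**Conclusion.** The concern holds for the TETRAS co-primary, and most directly for its sham-versus-orthosis comparison. Only the patient is blinded, no rater is masked, and the one safeguard has no stated masking, coverage or role in the endpoint. The false-positive risk of that test could rise from 0.0125 to about 0.05 with a lean of 1 point, or to about 0.5 with a lean of 3 points, at n = 21. These figures illustrate sensitivity. They rest on assumed leans and on the protocol's planning SD of 5, and they do not show that bias will occur.

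A reader might infer that the sham is useless or that both co-primaries are compromised. The documents do not support that: the sham still controls for weight and for the patient's placebo response, and the IMU amplitude does not depend on a rater. The sample size is unaffected. The point should still be settled before analysis, because unmasked scores cannot be masked afterwards, whereas stored videos can still be rescored.

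**What to change.** 1. For sham versus orthosis, define the TETRAS endpoint as the score that the independent neurologist already planned gives to the existing video clips of both devices, for every patient and task.
2. Amend the naming rule in section 11.1.3 so that the clips carry random codes in place of the condition. Show them in shuffled order and withhold the code list until the scores are locked.
3. Keep the coloured tabs covered or out of view; otherwise recoding does not mask.
4. Section 11.1.3 puts outside viewing of video under the principal investigator's supervision. Amend it so that the supervisor does not know the codes.
5. Keep the principal investigator's scores for eligibility and as a sensitivity analysis.
6. State that baseline versus orthosis cannot be masked on TETRAS because the device is visible. Have the same rater score the baseline clips, and interpret that comparison alongside the IMU result.
7. Section 3 says the study started in March 2022, so apply this to the stored videos before any analysis and notify the METC.

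The cost is an amendment, a recoding and shuffling step, and at least 175 minutes of playback (about 4.4 hours with baseline clips) plus scoring time. That time will be longer than playback, since Appendix I scores pouring, drinking and eating on two scales. The filming, the look-alike devices, the CRF software and the independent neurologist are already in the plan. No extra patients or visits are needed, and the videos stay in the hospital.

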## Tremor amplitude using IMU data

Tremor amplitude is measured during the performed tasks by taking the data from the IMU that is attached to the fingers. Likewise, this endpoint score will be compared over the two conditions using two-tailed matched pairs t-test, to analyze the difference in tremor amplitude. Again, the data will be checked for normal distribution, and the effect of the sham device will be evaluated.

The mean reduction in tremor severity according to both TETRAS rating and tremor amplitude of the hand are the co-primary endpoints. Sub analyses will be performed to evaluate the effect of the orthosis on these endpoints during the different tasks. This will be done to analyze the effect of the orthosis on specific tremor types: kinetic tremor (eating, drinking, pouring and spiral drawing), postural tremor (forward outstretched posture, lateral wing beating posture) and intention tremor (finger-to-nose).

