## 9.4 Prevention of missing data

Missing data will be prevented by checking all questionnaires on completeness and correctness before the patient leaves. To correct for missing data in questionnaires, missing data will be substituted by the weighted average. When data points of IMU sensors are missing, this will be substituted by making use of interpolation. If a patient is not able to perform a certain task, this will result in a complete missing data set from the IMU sensors and TETRAS score. That specific task for this specific subject will not be used in the data analysis. When two tasks or more cannot be performed, the data from the subject will be removed from the analysis.

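### IMU files carry the true device name into an analysis run mainly by the principal investigator; masking sham versus orthosis until the amplitudes are locked is a cheap safeguard

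*Protocol*

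**What the plan says.** Section 7.2 blinds the patient only: "Only the investigator can see which device is selected, thereby blinding the patient". It then fixes how recordings are filed: "Because the investigator knows which variant is being tested, the data will be placed with the corresponding variant in the digital CRF". It closes with "This eliminates the need to decode the collected data".

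Section 11.1.3 carries the label into the files: "The IMU/video data will be saved as followed: ID code", followed by task and condition, with an example that ends in the plain name of the baseline condition. On who analyses, it says: "Analysis of the clinical investigation data will primarily be executed by the principal investigator on the laptop".

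The same person has another role in section 7.3.4: "The principal investigator will quantify the tremor severity using the TETRAS scale". The only stated guard against investigator bias, a second neurologist's opinion, is in that section and concerns the rating. Nothing comparable is stated for the IMU data.

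Section 9.4 interpolates missing IMU points and removes a task that a patient cannot perform: "That specific task for this specific subject will not be used in the data analysis". It removes the subject when two or more tasks fail. For the IMU endpoint, section 9.1 says: "Again, the data will be checked for normal distribution, and the effect of the sham device will be evaluated". If the data are not normal, Wilcoxon tests replace the t-tests.

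**The concern.** Of the two co-primary endpoints, TETRAS is scored by someone who may know the device, while IMU amplitude needs no rater. Sham versus orthosis on the IMU endpoint is thus the comparison best placed to separate damping from weight, placebo response and rater expectation. Its advantage lasts only as long as the steps between raw signal and per-patient amplitude are also free of expectation.

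The protocol does not merely stay silent here. It states that the condition travels with the data and that no decoding is needed. Whoever interpolates a gap or extracts an amplitude sees from the file name whether it is sham or orthosis. At stake is the credibility of the objective endpoint, and some drift of error towards the device. Sample size is not affected.

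**Working it through.** **Inputs from the protocol.** Section 4.4 gives a two-tailed paired t-test, alpha 0.05/4 = 0.0125, dz = 0.8, power 0.8 and 21 evaluable patients. Section 7.1.1 gives seven tasks.

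**The plan's own figure.** dz = 4/√(5² + 5² − 2·0.5·5·5) = 4/5 = 0.8. The noncentrality is 0.8·√21 = 3.6661 and the critical t on 20 df is 2.7444. Power is 0.8100, as in Figure 3. The figure reproduces, so n = 21 and alpha = 0.0125 are used below.

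**Where judgement can enter.**

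| Step | What is fixed | What remains open with the label in view |
|---|---|---|
| Task removal (9.4) | Trigger is inability to perform; the task is dropped for that subject | Appendix I gives an ADL task that cannot be done a score of 4, so a failed pouring, drinking or eating task could be scored or removed |
| Gap filling (9.4) | Interpolation | Method and longest permitted gap |
| Amplitude extraction (7.1.1, 9.1) | One overall amplitude per task, from the finger sensor | Signal-processing settings |
| Choice of test (9.1) | t-test if normal, otherwise Wilcoxon | Which normality check decides |

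The settings in the last three rows may properly sit in an analysis plan that is not shown. The visible label is a rule of this protocol.

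**Size, by simulation under no effect.** Assumptions, not taken from the protocol: the difference for patient i on task j is u_i + e_ij, each part normal with variance 0.5 (between-task correlation 0.5), and the patient's value is the mean over tasks. Selective removal replaces the seven-task mean by the smallest of the seven possible six-task means, that is, the one most favourable to the device. Reject when |t| > 2.7444. The nominal rate is 1.25% two-sided, or 0.0125/2 = 0.625% in the device's favour.

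| Least favourable task removed in | Two-sided error | Error in the device's favour |
|---|---|---|
| no patient | 1.2–1.3% | 0.6–0.7% |
| 3 of 21 | 1.2–1.4% | 0.8–1.1% |
| 7 of 21 | 1.5–1.7% | about 1.3% |

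The ranges cover separate runs of 10,000 to 100,000 trials. For 3 of 21 they also cover whether the patients are arbitrary or are those in whom removal helps most; the last row uses arbitrary patients. Monte Carlo standard error at 10,000 runs is √(0.0125·0.9875/10,000) = 0.11 percentage points, so the two-sided change at 3 of 21 is hardly distinguishable from none. The shift in direction is clearer: at 7 of 21 the favourable error is 1.3/0.625, about twice nominal.

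Taking the smaller p-value of t-test and Wilcoxon, with no removal, gives about 1.4–1.5%.

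**The case against.** The trial is openly single-blind, so nothing is contradicted or miscalculated. That stands, and the point is an improvement rather than an error. But single-blinding explains why the person fitting the device knows it. It does not require the label to remain on the files during signal processing.

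Task removal is largely settled at the visit: a task that cannot be performed leaves no signal to inspect and discard. This mostly stands. What remains is the boundary between a failed task that is scored and one that is removed, and neutral file names alone would not settle that.

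A reader might infer that the 0.0125 level no longer holds, or that a positive IMU result cannot be told apart from analyst expectation. The documents do not support this. Error reaches about 2.4% only if one task may be dropped for everyone and the test chosen freely, and about 5 to 6% only if the worst task is dropped in every patient. Section 9.4 allows neither: removal is subject-specific and needs inability to perform. Section 9.1 gives a rule for the test, not a free choice.

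Masking would also be partial. The principal investigator reports adverse events during the whole visit (7.3.7) and may remember. Section 7.2 says only that the investigator sees the selected device, so the principal investigator's knowledge at the visit is an inference. The file names, however, reveal the condition to any analyst. Section 11.1.3 allows outside expert input on motion data, but nothing says the condition is masked in what is sent.

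**Conclusion.** The point holds as a low-cost improvement. By stated rule, IMU data keep the true device name and are analysed mainly by the person who also rates the patients, so processing decisions on the objective co-primary are not shielded from expectation. With occasional selective removal, two-sided error is about 1.2 to 1.7% against 1.25%, with the excess mostly in the device's favour. The level is unprotected, not lost.

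These sizes rest on the assumed correlation of 0.5, normal differences, equal weighting of tasks and deliberate choice of the least favourable task. The protocol gives no figure for how often judgement would be used, and bias from interpolation or amplitude extraction was not modelled.

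**What to change.** 1. In 7.2, replace the statement that decoding is unnecessary. In 11.1.3, replace the condition field of the IMU file name with a neutral per-patient code for the two devices, written by the CRF software, which already randomises and acquires the motion data. Baseline may stay labelled: it always comes first (7.3.5), so coding it hides little.
2. Record tasks not performed at the visit under a written rule that reconciles 9.4 with the score of 4 in Appendix I.
3. Complete interpolation and amplitude computation on coded files and lock that dataset.
4. Give the key to someone already on the study team who does not process the data, and keep it off the analysis laptop. The CRF log is unsuitable, because 11.1.2 stores it on the laptop that 11.1.3 names for the analysis. Merge the key only after lock.
5. Fix the test, or a named normality rule on the paired differences, in writing beforehand. It should not be chosen on coded data, because a per-patient random code scrambles the sign of the differences. For truly normal differences with standardised mean 2 and n = 21, simulated false rejection by Shapiro-Wilk at the 5% level rose from 6% to 44%.

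The cost is a changed label in the existing software, one merge step and a short delay before results by condition can be seen. No extra staff or patients are needed. Masking remains partial.
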